age- weight- and sex-matched subjects without diabetes using similar methods. Subjects <18 years of age or >65 years of age will not be studied.

Inclusion criteria – non-diabetic subjects.

We will recruit up to 20 weight-stable, non-diabetic subjects using the methods described above.

The following are **Exclusion Criteria:** -

- (a) Age < 25 or > 65 years (to avoid studying subjects who could have latent type 1 diabetes, or the effects of age extremes in subjects with normal or impaired fasting glucose).
- (b) HbA_{1c} ≥ 6.5%
- (c) Use of glucose-lowering agents.
- (d) For female subjects: positive pregnancy test at the time of enrollment or study
- (e) History of prior upper abdominal surgery such as adjustable gastric banding, pyloroplasty and vagotomy.
- (f) Active systemic illness or malignancy.
- (g) Symptomatic macrovascular or microvascular disease.

Subsequently, subjects will then undergo an Oral Glucose Tolerance Test to ensure that they have a fasting glucose ≤ 125mg/dl and a two-hour glucose ≤ 200mg/dl.

[figure not shown]
Inclusion criteria – diabetic subjects.

We will recruit up to 20 weight-stable, diabetic subjects treated with diet and lifestyle alone or with metformin monotherapy using the methods described above.

The following are **Exclusion Criteria:** -

- (a) Age < 25 or > 65 years (to avoid studying subjects who could have latent type 1 diabetes, or the effects of age extremes in subjects with normal or impaired fasting glucose).
- (b) Use of any glucose-lowering agent other than metformin.
- (c) 2 or more fasting glucose values > 250mg/dl on medication or after medication withdrawal.
- (d) Unwillingness or inability to withdraw medication for three weeks prior to, and for the duration of the study.
- (e) For female subjects: positive pregnancy test at the time of enrollment or study
- (f) History of prior upper abdominal surgery such as adjustable gastric banding, pyloroplasty and vagotomy.
- (g) Active systemic illness or malignancy.
- (h) Symptomatic macrovascular or microvascular disease.

The two groups will be matched for age, sex and weight.

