Experimental Design (Fig.4): A total of 40 subjects (20 with T2DM and 20 age- weight- and sex-matched subjects without diabetes) will undergo 2 experiments similar to those described in **Specific Aim 1** in random order. The two study days will be similar to the **Sal** and **Exe** days outlined in **Specific Aim 1**. The nondiabetic subjects will undergo two additional study days where at approximately 0600 (-180 min) an additional infusion of Intralipid (20%, 0.011ml/kg/min; Baxter, Healthcare, Deerfield, IL) and heparin (200 units prime, 0.2 unit/kg/min continuous) will commence as previously described⁵⁵. The infusion will continue till the end of study (1230 – 210 min). In previous experiments, these infusions raised FFA concentrations three-fold (~1200pmol/l) impairing insulin secretion and action as well as raising fasting and post-prandial glucagon concentrations²⁷. The two study days will be referred to as the **Sal+FFA** and the **Exe+FFA** study days.

Subjects with T2DM will undergo point of care glucose testing at 2000, 0000, and 0400. If the glucose value is found to be greater than 180 mg/dL, a mild correction scale as outlined in the existing “Subcutaneous Insulin Order Set” will be used to administer aspart insulin subcutaneously. The mild correction scale reads as follows: glucose 180-219 mg/dL, give 2 units, 220-259 mg/dL give 3 units, and so on up to 7 units of rapid acting insulin above 380 mg/dL. This order set also includes orders for nurses to check glucose at anytime if there is concern for hypoglycemia. If hypoglycemia is detected at any point, nurses will administer 15 grams of oral carbohydrate and recheck point of care glucose 15 minutes later to monitor for improvement in glucose and symptoms. The goal is to prevent morning glucose values above 180 mg/dL which have occurred after the standardized meal in some subjects with T2DM who control their diabetes with strict carbohydrate restriction. Administering subcutaneous insulin at 0400 would give sufficient time for exogenous insulin to be metabolized before blood draws are performed to measure endogenous insulin levels occur at 0830.

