Analytical Techniques: All blood will be immediately placed on ice, centrifuged at 4°C, separated and stored at -80°C until assay. Glucose will be measured using a Yellow Springs glucose analyzer. Glucagon will be collected in protease inhibitor-containing tubes (BD800, BD Franklin Lakes, NJ) and measured using an ELISA (Mercodia, Winston-Salem, NC). C-peptide will be measured using EMD Millipore (Billerica, MA) reagents. Insulin will be measured using a chemiluminescence assay with reagents obtained from Beckman (Access Assay, Beckman, Chaska, MN). Total and Intact GLP-1 will be collected in protease inhibitor-containing tubes (BD800, BD Franklin Lakes, NJ) and measured using an ELISA (ALPCO Diagnostics, Salem, NH). [3-³H]glucose specific activity will be measured by liquid scintillation counting after deproteinization and passage over anion- and cation-exchange columns⁴⁸. FFA concentrations will be measured using LC/MS as previously⁵⁶.

Power Calculation		Mean ± SD	Detectable difference
(n = 20 / 20)			
Φ (10 ⁻⁹ min ⁻¹) - hyperglycemia		149 ± 45	41 (28%)
Secondary Endpoints			
		Mean ± SD	Detectable difference
ϕ _b (10 ⁻⁹) - fasting		8 ± 2	1.8 (22%)
Fasting glucagon (ng/l)		71 ± 17	15 (21%)
Fasting glucose (mmol/l)		5.0 ± 0.4	0.4 (8%)
Fasting EGP (μmol/kg/min)		14.4 ± 2.2	1.5 (10%)
Φ (10 ⁻⁹ min ⁻¹) – GLP-1		316 ± 124	113 (36%)

Table 1: Means ± SD used to estimate power

the glucose, insulin and C-peptide concentrations observed during the experiments using the minimal model⁵⁷, incorporating age-associated changes in C-peptide kinetics⁵⁸. Φ is derived from the sum of ϕ₁ (1st phase insulin secretion) and ϕ₂ (2nd phase insulin secretion) as before⁵⁰. Disposition index (DI) will express β-cell function as a function of the prevailing insulin action⁴⁹. Glucose disappearance (Rd) will be calculated using steady state Steele equations^{59,60} after Specific activity is smoothed as previously described⁶¹. Endogenous glucose production (EGP) will be calculated as the difference between the tracer determined rate of glucose appearance and the glucose infusion rate. All infusion rates will be expressed as Kg per lean body mass. The GLP-1 model^{42,62}, will be used to quantify the potentiation of insulin secretion by GLP-1⁵¹. The model assumes that insulin secretion is linearly modulated by GLP-1 through an index (π), which quantifies the increase of insulin secretion due to (changes in) circulating GLP-1 concentrations⁵⁰.

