Statistical Analysis: The primary endpoints for the hypotheses being tested represent differences in a given parameter e.g. glucagon for each subject between the **Sal** and **Exe** days. These will be used in an analysis of covariance (ANCOVA), which will include the baseline value (**Sal**) as a covariate together with age, BMI and sex, to test for differences attributable to T2DM. Within-group differences attributable to study conditions will be assessed using a Student's paired *t*-test (parametric) or Wilcoxon matched-pairs signed rank test (non-parametric). Other response variables (e.g. hormone area under the curve) will also be examined.

Power Calculation: Please refer to **Table 1** for the relevant effect size that is detectable for fasting glucose, glucagon and EGP – since the primary analysis will use ANCOVA to detect between group differences in response to exendin-9,39 we anticipate the ability to detect even smaller changes in these parameters. As regards the ability to detect an effect on Φ – prior studies using a meal challenge show values of 50±17⁴⁵ vs. 29±19¹⁰ 10⁻⁹min⁻¹ – non-diabetic vs. T2DM respectively – a ~40% difference. Assuming similar between-group differences and similar variation in Φ, we will be amply powered to detect biologically significant variation in β-cell responses.

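### Table 1's detectable fasting glucose difference of 0.4 mmol/l (8%) rests on a non-diabetic spread, so it is unsupported for the T2DM versus non-diabetic comparison of this secondary endpoint

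*Combined protocol and SAP*

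**What the plan says.** Table 1 is captioned "Means ± SD used to estimate power". Its fasting glucose row, listed among the secondary endpoints, has one mean and SD (5.0 ± 0.4 mmol/l) and a detectable difference of 0.4 (8%) for n = 20/20. It names no source population and has no separate T2DM entry.

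The Power Calculation paragraph sends the reader to this table "for the relevant effect size that is detectable for fasting glucose, glucagon and EGP". Because the main analysis is an ANCOVA of between-group differences in response to exendin-9,39, it continues, "we anticipate the ability to detect even smaller changes in these parameters". For Φ the same paragraph quotes separate non-diabetic and T2DM values (50±17 and 29±19). For glucose it does not.

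Under Statistical Analysis, the analysed quantities are "differences in a given parameter e.g. glucagon for each subject between the" Sal and Exe days, with the Sal value, age, BMI and sex as covariates.

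Three places describe glucose in the T2DM group:
- The Medication withdrawal paragraph has metformin stopped three weeks before the study and throughout it.
- The exclusion criterion for diabetic subjects is "2 or more fasting glucose values > 250mg/dl on medication or after medication withdrawal".
- On the overnight glucose checks, Experimental Design says: "The goal is to prevent morning glucose values above 180 mg/dL which have occurred after the standardized meal in some subjects with T2DM".

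Non-diabetic subjects must have a fasting glucose of at most 125 mg/dl.

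**The concern.** The SD that fixes the glucose row appears to come from people with normal glucose, while the row is offered for a comparison in which half the subjects have untreated T2DM. If the T2DM group is more variable on the scale analysed, the design detects only larger differences than the table prints. The ANCOVA remark then promises an improvement on a figure that has no valid starting point.

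This matters for interpretation. If the primary glucagon result is positive, the Interpretation section next asks whether fasting glucose changed too. Its explanations for unchanged glucose are physiological: compensatory insulin secretion, or a matched rise in glucose disappearance. Limited sensitivity is not among them. A reader who trusts 0.4 mmol/l could give a null glucose result more weight than the trial can support.

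**Working it through.** **Inputs.** From the documents: 20 per group; 5.0 ± 0.4 mmol/l; limits of 125, 180 and 250 mg/dl. Alpha and power are not stated; I assume two-sided 0.05 and 80%. The documents give no T2DM SD, no SD of the Exe–Sal change, no day-to-day correlation (ρ) and no between-group gap in Sal glucose. Values used for these are assumptions.

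**1. The plan's figure.** For a two-sample t-test with 20 per group (38 df), the detectable difference is 0.909 × SD. With SD 0.4 this is 0.364 (0.354 by the normal approximation), which rounds to 0.4, and 0.4/5.0 = 8%. The same multiplier gives Φ 40.9 (printed 41), ϕb 1.82 (1.8), Φ with GLP-1 112.7 (113) and glucagon 15.5 (15; the normal approximation gives 15.06). Only EGP does not fit (2.0 against 1.5 printed). The glucose arithmetic is sound, and it compares levels.

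**2. Whom the input describes.** Mean + 3 SD = 5.0 + 3 × 0.4 = 6.2 mmol/l. At 18.016 mg/dl per mmol/l:
- The non-diabetic ceiling is 125/18.016 = 6.9 mmol/l.
- The morning values already exceeded in some T2DM subjects are 180/18.016 = 10.0 mmol/l, which is (10.0 − 5.0)/0.4 = 12.5 table SDs above the table mean.
- The T2DM exclusion threshold, which needs two or more values, is 250/18.016 = 13.9 mmol/l.

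The input fits the non-diabetic group and not the T2DM group.

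**3. The table's method with a T2DM SD.** Keep controls at 0.4 and pool: SDp = √((0.4² + SD_T2DM²)/2). The result still rounds to 0.4 while 0.909 × SDp < 0.45, so SDp < 0.495 and SD_T2DM < √(2 × 0.495² − 0.4²) ≈ 0.57 mmol/l.

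| Assumed T2DM SD | SDp | Detectable difference | Power at 0.4 |
|---|---|---|---|
| 1.0 | 0.762 | 0.69 | 37% |
| 1.5 | 1.098 | 1.00 | 20% |
| 2.0 | 1.442 | 1.31 | 14% |

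**4. The planned analysis.** For the change adjusted for Sal, with equal SDs on both days and the same ρ in both groups, the residual SD is SDp × √(1 − ρ²). The detectable difference is 0.909 × that:

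| Assumed T2DM SD | ρ = 0.5 | ρ = 0.8 | ρ = 0.9 |
|---|---|---|---|
| 1.0 | 0.60 | 0.42 | 0.30 |
| 1.5 | 0.86 | 0.60 | 0.44 |
| 2.0 | 1.14 | 0.79 | 0.57 |

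**5. Collinearity.** Sal glucose should differ markedly between the groups, so adjusting for it widens the standard error of the group effect. The multiplier is √(1 + gap²/(0.1 × SSW)), where 0.1 = 2/20 and SSW is the within-group sum of squares of Sal. For T2DM SD 1.5, SSW = 19 × (0.16 + 2.25) = 45.8. A gap of 2 mmol/l gives √(1 + 4/4.58) = 1.37, and 3 mmol/l gives √(1 + 9/4.58) = 1.72. At ρ = 0.9 the 0.44 above (0.435 unrounded) becomes about 0.60 to 0.75.

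**The case against.** The strongest reply is that the spread of glucose levels is the wrong yardstick. The trial analyses each subject's Exe–Sal change with Sal as a covariate, and high morning values say little about how variable that change is. This stands. With T2DM SD 1.0 and ρ = 0.9, step 4 gives 0.30 mmol/l, better than printed. A reader might infer that the 20/20 design fails to deliver 0.4 mmol/l. The documents do not support that, because they give neither the SD of the change nor ρ. Step 5 shows only that the favourable cells cannot be taken at face value.

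It is also fair that 250 mg/dl is an exclusion threshold rather than a study-morning distribution, and that the overnight checks and correction insulin are meant to prevent values above 180 mg/dl. They may narrow the spread, but the plan does not say by how much. Correction may also differ between a subject's two nights, so a high ρ cannot be presumed.

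A reader might further infer that the plan would take a null glucose result as proof of compensation. It does not go that far: the Interpretation section offers compensation as one possibility, measures glucose appearance and disappearance by tracer, and compares EGP with insulin.

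Finally, fasting glucose is secondary, and the ANCOVA remark is worded as an expectation. Both points limit the weight of the finding without supplying the missing input.

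**Conclusion.** The point holds as a lack of support, not as a demonstrated shortfall. The 0.4 mmol/l (8%) follows correctly from 5.0 ± 0.4, but that input does not describe the T2DM half of the comparison, and the expectation of detecting still smaller changes has no number behind it for glucose.

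On the table's own method the figure survives only for a T2DM SD up to about 0.57 mmol/l. For the planned analysis the range is about 0.30 to 1.14 mmol/l (T2DM SD 1.0 to 2.0, ρ 0.5 to 0.9), before a collinearity multiplier of about 1.4 to 1.7 for a gap of 2 to 3 mmol/l at T2DM SD 1.5. So 0.4 may or may not be reached. These ranges rest on assumed SDs, correlations and gaps, and on two-sided 0.05 with 80% power. That the input is non-diabetic is inferred from its size; Table 1 does not name the source. The point is worth correcting for a secondary endpoint and does not touch the primary test of fasting glucagon.

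**What to change.** - Recompute the glucose row for the planned ANCOVA from the SD of the Exe–Sal change in each group, allowing for the collinearity of Sal glucose with group. State alpha, sidedness and power.
- If no reliable T2DM SD is available (the Background section itself calls the preliminary sample small), show a range over plausible SDs and correlations. Otherwise label the row as based on non-diabetic data.
- Take fasting glucose out of the statement that smaller changes are expected to be detectable.
- In the Interpretation section, commit to reporting the confidence interval for the between-group difference in glucose change, and to reading it before treating unchanged glucose as physiology.

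This is an edit to one table row and two paragraphs, with no extra subjects or visits. The price is a stated sensitivity that will probably look less favourable.

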had shown heterogeneity in glucagon suppression to hyperglycemia in subjects across the spectrum of glucose tolerance – with some of the heterogeneity explained by impaired insulin action⁵². In our preliminary experiments in people with T2DM, inhibition of endogenous GLP-1 secretion by exendin-9,39 raised both fasting and nadir glucagon in response to an intravenous glucose profile that mimics the systemic appearance of a 50g OGTT⁴⁰ (**Fig.1**). If this is the case, then we will accept our 2° hypothesis (i). It is possible that the nadir observed is a reflection of fasting glucagon concentrations and therefore we will also compare the % suppression from fasting values to determine whether effects on α -cell suppression by hyperglycemia are due to differences in dysregulation of baseline glucagon secretion. If we reject our 2° hypothesis (i), we will design studies to determine if α -cell suppression in response to protein and fat (greater stimuli of post-prandial glucagon secretion) is also impaired by GLP1R blockade with exendin-9,39. This is relevant to people with T2DM who have paradoxical rises in glucagon after mixed meals which cause postprandial hyperglycemia^{63,64}.

The relative disparity in response (between people with and without T2DM) to exendin-9,39 in the fasting state observed previously may reflect the underlying degree of β -cell dysfunction. People with T2DM have impaired β -cell function perhaps to the degree that they are much less responsive to any change in endogenous GLP-1 secretion and action – reflecting a general decreased response to secretagogues^{65,66}. Accordingly, we will test our 2° hypothesis (ii) by comparing the change in Φ (T2DM vs. non-diabetic controls) between **Sal** and **Exe** days during the hyperglycemic clamp. If we accept our hypothesis, in the non-diabetic subjects, we will correlate the change in Φ with β -cell function as measured by the Disposition Index⁴⁹ (calculated from the screening OGTT⁶⁷) to determine if the effect of exendin-9,39 on insulin secretion is a function of baseline DI. We would expect the effect of GLP1R blockade on Φ to be less marked as DI decreases. Examination of the effect on the different components of Φ i.e. ϕ_1 and ϕ_2 will enable us to determine whether these effects occur via increased storage of preformed insulin granules (ϕ_1 – 1st phase), increased synthesis during a challenge (ϕ_2 – 2nd phase), or a combination.

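### The planned correlation of the change in Φ with DI cannot tell lower responsiveness at low DI from the same percentage effect on a smaller baseline Φ

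*Combined protocol and SAP*

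**What the plan says.** The passage is in section IV, Interpretation, in the paragraph on 2° hypothesis (ii). Once that hypothesis is accepted, "in the non-diabetic subjects, we will correlate the change in Φ with β -cell function as measured by the Disposition Index", with DI "calculated from the screening OGTT". The purpose is "to determine if the effect of exendin-9,39 on insulin secretion is a function of baseline DI", and the stated expectation is "We would expect the effect of GLP1R blockade on Φ to be less marked as DI decreases".

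Three other statements bear on how this is read:

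- **Scale.** The Statistical Analysis paragraph says that the primary endpoints "represent differences in a given parameter e.g. glucagon for each subject between the" Sal and Exe days. The word absolute is not used, and no percentage or log scale is given for Φ.
- **Baseline adjustment.** The Sal value enters the ANCOVA "as a covariate together with age, BMI and sex, to test for differences attributable to T2DM". It is not mentioned for the correlation within the non-diabetic group.
- **DI.** The text on calculations in section IV states: "Disposition index (DI) will express β-cell function as a function of the prevailing insulin action". Secretion is therefore one component of DI and insulin action is the other.

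For glucagon, the same Interpretation section foresees that a nadir may only mirror the fasting level, and adds a relative check: "we will also compare the % suppression from fasting values". Φ has no counterpart.

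**The concern.** The correlation is meant to probe a mechanism: that weaker β-cells respond less to endogenous GLP-1, which would explain a smaller effect of blockade in T2DM. A difference in Φ mixes two things, the fraction of secretion removed and the amount of secretion there was to remove. If the fraction is the same in everyone, subjects with low Φ still show a small difference. Because Φ is part of DI, subjects with low DI may tend to have low Φ. A correlation in the expected direction could then be taken as support for the mechanism although responsiveness does not vary with DI.

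**Working it through.** **Inputs from the documents.** Φ under hyperglycemia is 149 ± 45 with a detectable difference of 41, or 28% (Table 1). There are up to 20 non-diabetic subjects.

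**Assumptions, none given in the documents.** DI = Φ × SI, where SI is insulin action; CV of SI 30% or 50%; correlation ρ between log Φ and log SI from 0 to −0.8; correlation of OGTT Φ with clamp Φ 1 or 0.7; error of Φ 10% per study day; Φ lognormal.

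**1. The plan's own figure.** A two-sample t-test with 20 per group, two-sided 0.05 and 80% power (both assumed) gives a detectable difference of 40.9, so the 41 is reproduced. It is a between-group figure. The 28% serves below only as a plausible size of fall. The documents give no figure for the DI correlation.

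**2. Uniform percentage fall.** With Φ_Exe = (1 − f) × Φ_Sal, the fall is f × Φ_Sal. At f = 0.28:

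- Φ = 104 (mean − 1 SD): 0.28 × 104 = 29
- Φ = 149 (mean): 0.28 × 149 = 42
- Φ = 194 (mean + 1 SD): 0.28 × 194 = 54

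Without measurement error, the correlation of the fall with DI is exactly corr(Φ_Sal, DI), whatever the value of f.

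**3. When the sign is as expected.** On the log scale, cov(log Φ, log DI) = s² + ρ·s·s_SI, where s and s_SI are the SDs of log Φ and log SI. It changes sign at ρ = −s / s_SI. The CV of Φ is 45/149 = 0.302, so s = √ln(1 + 0.302²) = 0.295. For a CV of SI of 50%, s_SI = √ln(1 + 0.5²) = 0.472 and the sign changes at ρ = −0.63. For 40% it changes at −0.77. For 30% the value is −1.01, so it never changes.

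**4. Simulation at n = 20, f = 28%, 10% error per day.** The significance threshold is |r| = 0.444 (two-sided 0.05). Each cell gives the mean correlation of the absolute fall with DI and, in brackets, the share of runs significant in the expected direction. The nominal share is 2.5%.

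| CV of SI | ρ | OGTT Φ tracks clamp Φ fully | correlation 0.7 |
|---|---|---|---|
| 30% | 0 | 0.37 (41%) | 0.26 (22%) |
| 30% | −0.3 | 0.31 (29%) | 0.22 (17%) |
| 30% | −0.6 | 0.23 (18%) | 0.17 (12%) |
| 30% | −0.8 | 0.17 (11%) | 0.12 (8%) |
| 50% | 0 | 0.27 (24%) | 0.19 (15%) |
| 50% | −0.3 | 0.16 (12%) | 0.11 (8%) |
| 50% | −0.6 | 0.02 (3%) | 0.01 (3%) |
| 50% | −0.8 | −0.15 (1%) | −0.10 (1%) |

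Between the listed rows, with CV of SI 50% and full tracking, ρ = −0.5 gives a mean of 0.07 (about 5% significant) and ρ = −0.7 gives −0.05. With a 15% fall, the largest mean is 0.20 (18% significant).

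**5. The same model on the relative scale.** For log(Φ Sal / Φ Exe) against log DI, the mean correlation is about 0.00 and 2% to 3% of runs are significant, in every scenario. Reversing the ratio changes only the sign.

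DI comes from the screening OGTT, a different day from Sal and Exe, so shared measurement error is not the source of the pattern. The scale of the change is.

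**The case against.** The strongest reply is that the pattern depends on an input nobody has. A reader might infer that the planned analysis would confirm its expectation whatever the truth. The documents do not support that. They do not report how Φ relates to DI among non-diabetic subjects, and DI also contains insulin action. Someone with high Φ and low insulin action need not have a high DI, and steps 3 and 4 show the correlation vanishing or reversing when that compensation is strong. Measurement error and a sample of 20 also mean that it would often miss significance. All of this stands, so the accurate word is could.

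Second, this is a conditional follow-up. Hypothesis (ii) is tested by comparing the change in Φ between groups, with the Sal value as covariate. A reader might infer that this test shares the defect, but the point concerns only the correlation within the non-diabetic group. This also stands.

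Third, scale is a choice. No passage says that blockade acts multiplicatively. If effect means the amount of secretion lost, a smaller loss at low DI is a true statement. If the true effect were a constant fall of 42, the ratio scale would mislead in the other direction: 42/104 = 40% at low Φ against 42/194 = 22% at high Φ. This stands as a reason to show both scales and not to discard the absolute one. It does not rescue the absolute change as the sole basis for a claim about responsiveness.

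Finally, reading the change as a difference is an inference from the Statistical Analysis paragraph. If a relative change is intended, the text should say so.

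**Conclusion.** The concern holds in a limited form. As written, the correlation cannot separate reduced responsiveness at low DI from an equal percentage effect on a smaller baseline, and no stated safeguard covers it. For a uniform 28% fall with 10% daily error and OGTT Φ tracking clamp Φ, the mean spurious correlation is about 0.07 to 0.37, significant in about 5% to 40% of runs, as long as compensation between Φ and insulin action is not strong. Beyond that it falls to zero or turns negative, and could then hide a real dependence on DI. These sizes rest on the assumed form of DI, the assumed variation in insulin action and the assumed error. Only Φ, its SD, the 28% and the sample size come from the plan. What is at stake is one mechanistic interpretation, not the primary result or the result for hypothesis (ii).

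**What to change.** In the Interpretation paragraph on 2° hypothesis (ii), state that the change in Φ will be correlated with screening DI on two scales: the Sal-to-Exe difference and log(Φ Exe / Φ Sal). Do the same for φ1 and φ2. Report both, and conclude that responsiveness depends on baseline DI only if the relative change shows it too. This carries over to Φ the check on relative change already planned for glucagon.

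The cost is a sentence or two of analysis text, with no extra subjects, visits or assays. It should be written before the Φ results are seen, because a scale chosen afterwards would carry little weight. The small downside is that the ratio overstates the effect at low Φ if the true effect is additive, which is why the absolute change stays beside it.
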